# Patient Reported Side Effects Dose Delays or Adjustments

[figure not shown]
- Side Effect Acceptability ratings are defined in section 3.4.2. Patient reported side effects (i.e., dizziness, lightheadedness, bad dreams, nausea, vomiting, itchiness, and hallucinations: all are dichotomous outcomes). These side effects will be evaluated based on patient-specific reports of how "acceptable" or "unacceptable." Patients reporting side effects and rating them as "unacceptable" will follow the dose delay or adjustment described in the Table 1. If side effects are rated "acceptable" then no dose delays or adjustments will occur.
- Figure 3 Decision Chart for Acceptability Based dose revisions.

Table 1. Loading and Maintenance Dose Adjustment Procedures:

Systolic blood pressure <80 or >160, Heart rate <40 or >120  Monitor for 5 minutes minutes for symptom resolution  Monitor for 5 minutes for symptom resolution  If event does not resolve  Hold infusion for 5 box (e.g., 0.05mg/kg/hr) and continue infusion.  If event does not resolve  Hold infusion for 5 box (e.g., 0.05mg/kg/hr) and continue infusion.  May D/C infusion and monitor subject for safety as	Event	1st Action	2 nd 1	Action	3rd /	Action	If event does not resolve
Pressure <80 or >160,   Heart rate <40 or >120   Heart rate <40 or >1							
monitor subject for safety as described in Section 7.4 and described in Section 7.4 and 7.5  Event qualifies as DLT	pressure <80 or >160,	labetalol or hydralazine per managing anesthesiologist Monitor for 5 minutes for symptom	for 5 minutes - symptom recheck at 5	(e.g., 0.05mg/kg/hr reduced to 0.025 mg/kg/hr) and continue	for 5 minutes - symptom recheck at 5 minutes:  May D/C infusion based on investigator discretion and monitor subject for safety as described in Section 7.4 and	(e.g., 0.025mg/kg/hr reduced to 0.013 mg/kg/hr) and continue	minutes of unresolved hemodynamic effect:  D/C infusion and monitor subject for safety as described in Section 7.4 and 7.5  Event qualifies

Event	1st Action	2 nd A	Action	3rd A	Action	If event does not resolve
		If event does not resolve	If the event resolves	If event does not resolve	If the event resolves	 1650.776
If RASS -2 or below, OR Respiratory Rate is < 8	Hold infusion for 10 minutes - symptom recheck every 10 min until resolution	If no resolution within 1 hour:  D/C infusion based on investigator discretion and monitor subject for safety as described in Section 7.4 and 7.5	↓ dose by 50% (e.g., 0.05mg/kg/hr reduced to 0.025 mg/kg/hr) and continue infusion.	If no resolution within 1 hour:  D/C infusion based on investigator discretion and monitor subject for safety as described in Section 7.4 and 7.5	↓ dose by 50% (e.g., 0.025mg/kg/hr reduced to 0.013 mg/kg/hr) and continue infusion.	D/C infusion and monitor subject for safety as described in Section 7.4 and 7.5 Event qualifies as DLT
Dizziness, lightheadedness, bad dreams, persistent itchiness, hallucinations, nausea, vomiting, or other side effects rated by patient as Not Acceptable	Hold infusion for 10 minutes - symptom recheck every 10 min until resolution Supportive care medications in 9.1	If no resolution within 1 hour:  D/C infusion based on investigator discretion and monitor subject for safety as described in Section 7.4 and 7.5	↓ dose by 50% (e.g., 0.05mg/kg/hr reduced to 0.025 mg/kg/hr) and continue infusion.	If no resolution within 1 hour:  D/C infusion based on investigator discretion and monitor subject for safety as described in Section 7.4 and 7.5	↓ dose by 50%     (e.g.,     0.025mg/kg/hr     reduced to 0.013     mg/kg/hr) and     continue     infusion.	D/C infusion and monitor subject for safety as described in Section 7.4 and 7.5 Event qualifies as DLT
Nausea or Vomiting	Rescue medications as indicated in 6.6  Re-evaluate for symptom resolution 10 min after rescue medication  Hold infusion for 10 minutes - symptom recheck every 10 min until resolution	If no resolution within 1 hour:  D/C infusion based on investigator discretion and monitor subject for safety as described in Section 7.4 and 7.5	dose by 50%  (e.g., 0.05mg/kg/hr  reduced to 0.025  mg/kg/hr) and  continue  infusion.	If no resolution within 1 hour:  D/C infusion based on investigator discretion and monitor subject for safety as described in Section 7.4 and 7.5	dose by 50%  (e.g., 0.025mg/kg/hr  reduced to 0.013  mg/kg/hr) and  continue  infusion.	D/C infusion and monitor subject for safety as described in Section 7.4 and 7.5 Event qualifies as DLT

Figure 3. Dose adjustments based on patient-reported acceptability

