# Events that Trigger Dose Adjustment Procedures:

- Persisting unresolved hemodynamic side effects defined as Systolic blood pressure <80 or >160,
   Heart rate <40 or >120^33
  - o Unresolved after 3 consecutive measurements within a 15-minute interval
- Persisting (i.e., unresolved within 1 hour of onset) side effects sedation, dizziness, lightheadedness, persistent itchiness, bad dreams, hallucinations, or other side effects that are reported as not acceptable to patients or clinicians, despite minimizing infusion rate.
- Table 1 includes procedures for dose adjustments.

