### 9 Protection Against Risks

# 9.1 Management of drug related toxicity

The PI is a practicing, board-certified clinical anesthesiologist with extensive experience in the administration of this study drug under normal clinical circumstances. The study drug will be started during routine anesthesia care where monitoring is the strictest and closest, thereby enabling early detection of any safety events. The patients will remain monitored in an appropriate care environment throughout the duration of the 12-hour drug infusion, enabling timely detection and treatment of any serious events should they occur. Staff will also be trained to be familiar with common and uncommon side/adverse events for reporting.

Supportive care drugs that may be used in the event of drug related toxicity:

- Event: Persisting unresolved hemodynamic side effects defined as Systolic blood pressure <80 or >160, heart rate <40 or >120, unresolved after 3 consecutive measurements within a 15-minute interval
  - Supportive care medications:
  - Labetalol 10-20mg IVP or Hydralazine 10-25mg IVP p.r.n. hypertension at discretion of managing anesthesiologist.
- Event: Persisting side effects sedation, dizziness, lightheadedness, bad dreams, hallucinations, or other side effects that are reported as not acceptable to patient or clinicians, despite minimizing infusion rate
  - Supportive care medications:
  - o Midazolam 1-4mg IVP p.r.n. dysphoria, at discretion of managing anesthesiologist.

Refer to Section 6.8 for Rescue Drugs.

Refer to Section 6.3 of the protocol for instructions on dose delays and modifications.

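### Section 6.3 contradicts itself on whether the patient alone, or also a clinician, can start dose adjustment, and the DLT status of a clinician-triggered stop is left open

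*Combined protocol and SAP*

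**What the plan says.** Section 6.3 states the entry rule for dose adjustment in three places.

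- **Events that trigger dose adjustment.** The list covers "Persisting (i.e., unresolved within 1 hour of onset) side effects sedation, dizziness, lightheadedness, persistent itchiness, bad dreams, hallucinations", and continues "or other side effects that are reported as not acceptable to patients or clinicians, despite minimizing infusion rate". It then refers to Table 1.
- **Patient-reported side effects.** The scope is "Patient reported side effects (i.e., dizziness, lightheadedness, bad dreams, nausea, vomiting, itchiness, and hallucinations: all are dichotomous outcomes". These effects are judged on the patient's own rating. An unacceptable rating leads to Table 1. For the opposite case the text is flat: "If side effects are rated 'acceptable' then no dose delays or adjustments will occur".
- **Table 1.** The row for these symptoms ends with "other side effects rated by patient as Not Acceptable". It has no entry for a clinician's judgement. A separate nausea or vomiting row gives rescue medication, re-evaluation and a hold, with no acceptability condition. Sedation has its own row: "If RASS -2 or below, OR Respiratory Rate is < 8".

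Sections 6.2 and 7.3 leave rate changes to the study team's judgement. Section 9.1 repeats the two-rater wording ("or other side effects that are reported as not acceptable to patient or clinicians") when it lists supportive medication, and refers back to section 6.3 for dose changes. Section 3.4.1 defines a DLT as a persisting hemodynamic effect, or a complete stop of the infusion because of the patient's acceptability ratings.

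**The concern.** Disagreement between patient and clinician is foreseeable. Under section 3.4.2 the patient's rating asks whether she would take part again, which is not what a clinician judges at the bedside. The protocol also brings clinicians in: abnormal diary responses alert staff, and an LSD score above 8 prompts a bedside evaluation (Appendix 2). When the two disagree, one paragraph starts the adjustment sequence and the next forbids it, and nothing says which prevails.

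Two things are at stake. Patients with the same presentation may be handled differently depending on which paragraph the team follows. And a stop that begins with a clinician's judgement has no settled DLT status, in a design where a few DLTs decide the dose.

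**Working it through.** The plan gives no figure on this point to reproduce. The check is a comparison of the passages, one timing calculation and one count.

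**1. One case put through each rule.** Take a patient whose hallucinations have lasted more than an hour. She rates them acceptable and the clinician does not.

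- Section 6.3, trigger list: she qualifies and goes to Table 1.
- Section 6.3, patient-reported paragraph: no delay or adjustment.
- Table 1, side-effect row: not entered, because her own rating is acceptable.
- Sections 6.2 and 7.3: the study team may change the rate.

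The first and second cannot both be followed, and the first sends her to a table with no row for her. The trigger list also presupposes that the rate has already been minimized, a step the second rule excludes for this patient. The result is the same for dizziness, lightheadedness, bad dreams and itchiness.

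**2. Nausea and vomiting.** The patient-reported paragraph makes adjustment depend on her rating. The separate Table 1 row includes a hold whatever the rating. A patient who vomits and rates it acceptable therefore comes under a hold by one rule and no delay by the other.

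**3. When the clinician trigger can operate.** Inputs: the load lasts 60 minutes (section 1); the switch to maintenance may come up to 15 minutes late, so at most 75 minutes (section 6.2); persistence means unresolved within 1 hour of onset (section 6.3). For onset at t minutes after infusion start, the earliest trigger is t + 60.

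- 60-minute load: t + 60 is at least 60 for every t of 0 or more, so the trigger falls at or after the end of the load.
- 75-minute load: t + 60 < 75 requires t < 15, so only an onset in the first 15 minutes can trigger during the load.

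The conflict over clinician judgement therefore lies mainly in maintenance.

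**4. DLT status.** Section 3.4.1 measures the primary outcome for 24 hours from infusion start, so events in maintenance count. A clinician-triggered patient taken to the end of Table 1 is labelled a DLT there. Under section 3.4.1 a non-hemodynamic stop counts only if the patient's ratings caused it, and hers did not. By the same section, two DLTs in a cohort of 3 to 6 end escalation. One patient is 1/6 = 17% to 1/3 = 33% of a level. If one other DLT has already occurred at the level:

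- 6 patients: 1/6 = 17% if her case is not counted, 2/6 = 33% if it is.
- 3 patients: 1/3 = 33% if not counted, 2/3 = 67% if it is.

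In both, the level stays open under one definition and closes under the other.

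**The case against.** The strongest reply is that the mismatch is narrow and mostly outside the tested variable. The MTD variable is the loading dose, the one-hour condition puts the clinician trigger largely after the load, and a hold or a 50% cut is not itself a DLT. All of that stands, and it limits the point to safety handling and to stops that reach the end of Table 1. Figure 3, the acceptability decision chart, is not visible in the text available and might settle precedence; its caption names only patient-reported acceptability.

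A reader might infer more than the documents support:

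- **That a sedated patient is caught in the conflict.** Sedation is not in the patient-rated list, and RASS -2 or below has its own row that ignores the rating. Only lighter sedation is unclear.
- **That vomiting can enter Table 1 only on the patient's rating.** It has the separate unconditional row, which is a different conflict.
- **That the tested load is cut.** A clinician-triggered hold from minute 15 to 25, then half rate, would leave (15 + 35 x 0.5)/60 = 54% of the load. The one-hour condition rules out a clinician trigger at minute 15.
- **That clinicians have no route to act.** Sections 6.2 and 7.3 give the study team discretion. This removes the claim but adds to the contradiction, because discretion does not fit a flat statement that no adjustment will occur.
- **That section 9.1 is a second dose-adjustment rule.** It concerns supportive medication; its wording is only parallel.
- **That the patient's rating is unreliable under ketamine.** The documents do not say so, and the point does not need it.

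**Conclusion.** The contradiction is in the text and is more than missing detail, since the two rules of section 6.3 give opposite instructions for the same patient. It covers five symptoms, with a related conflict for nausea and vomiting. It bears on safety handling, mainly during maintenance, and on DLT classification. No conclusion is drawn about the share of the load delivered.

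One case can move an escalation decision if a patient is stopped on a clinician's judgement at the end of Table 1 while rating the effect acceptable, and one other DLT has occurred at that level. How often this would happen cannot be estimated from the documents. The conclusion also assumes that Figure 3 does not resolve the precedence.

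**What to change.** - Reconcile the trigger list, the patient-reported paragraph and Table 1 in section 6.3, and the parallel wording in section 9.1, so that all name the same rater or raters. Include the nausea or vomiting row, and make the text consistent with the discretion in sections 6.2 and 7.3.
- Align section 3.4.1 and Table 1 on whether a clinician-triggered stop is a DLT.
- Record in the CRF who triggered each adjustment (patient, clinician or both), and report clinician-triggered adjustments separately from the patient-rated acceptability endpoint.

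Which clinical rule prevails is for the sponsor to decide. The cost is wording in a few sections and one CRF field, with no extra patients or visits.

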# 3.4 Endpoints

# 3.4.1 Primary Endpoint

Maximum Tolerated Dose (MTD). The MTD will be defined as the dose at which fewer than 33% of patients experience a DLT defined by intolerability.

Tolerability (dichotomous Yes/No)

Tolerability (YES) will be defined as: lack of adverse events (adverse event defined as: severe unresolved hemodynamic effect: systolic blood pressure <80 or >160, heart rate <40 or >120).

Lack of Tolerability will be defined as presence of any adverse event (i.e., severe unresolved hemodynamic effect: systolic blood pressure <80 or >160, heart rate <40 or >120).

A **DLT** event is defined by complete infusion cessation due to intolerable side effect acceptability ratings by patient, OR the experience of an intolerable event as defined above. The escalation of dosing will be as noted in Figure 2 and is based on a modified Fibonacci sequence  $^{101,102}$  with smaller proportional increases in dose in the escalation scheme. Escalations occur until 2 in a cohort of 3 to 6 experiences DLT (i.e., until  $\geq$ 33% of patients experience DLT at that dose). The dose **below** this level estimates the MTD.

Participants will be classified as having had a DLT if any of the following conditions are met:

- Persisting (i.e., unresolved after 3 consecutive measurements within a 15-minute interval)
  hemodynamic side effects defined as below and despite treatments or minimizing
  infusion rates as specified.
  - Systolic blood pressure <80 or >160
  - Heart rate <40 or >120
- Complete infusion cessation due to intolerable side effect acceptability ratings by patient

Primary Outcomes will be measured at a minimum of every 4-hours from the start of the ketamine infusion (t = 0) for 24-hours (12-hours post infusion cessation). Additional assessments will be administered between the 4-hour measurements if any adverse event or side effect is noted by the patient.

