#### 5.5 Screen Failures

Participants who are consented to participate in the third trimester of pregnancy, may be withdrawn from the study protocol before, during, or following the cesarean surgery if events arise such as to preclude them from participating in the remainder of the study. These participants will be considered "Screening Failures". The following list is non-comprehensive, but represents the most likely scenarios:

- Vaginal or non-cesarean delivery
- Development of exclusion-based criteria prior to cesarean surgery (i.e., severe preeclampsia, preterm delivery, NICU assessment likely, etc.)
- Severe complications during labor and/or delivery whereby the PI and/or patient's surgeon recommend a change in therapeutic response.

Withdrawn participants will be replaced at a proportion of 1:1. Procedures are as follows:

- Study personnel and investigators will be notified.
- Written documentation of withdrawal and reason for withdrawal will be noted per IRB protocol.
- Study personnel, investigators, and pharmacy will be informed of the need for replacement of pharmaceuticals due to participant withdrawal.
- Subsequent data to be collected from the withdrawn participant will be restricted to the minimum amount necessary to continue to monitor safety, i.e., side effect diary including questions of sedation, LSD short form, dizziness, lightheadedness, bad dreams, nausea, vomiting, pruritus, hallucinations.

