#### Side Effects.

Monitoring during the infusion will follow our clinical standards of perioperative ketamine monitoring. A maternal side effect digital diary will also be used. The digital diary has been previously developed and tested in our preliminary lactation volunteer study. The diary alerts questions to patients include the Richmond agitation-sedation scale (RASS), dysphoria (LSD short form^105), and side effects. Automated alerts for abnormal responses go to clinical and research staff for immediate action. Any report of side effects will trigger a blood draw for analysis and correlation to measured plasma levels.

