Appendix 2 – Schedule of Perinatal, Surgical, and Infusion-Specific Research Activities

			Study Visit# 1; Day 0—Delivery/Cesarean Surgery -24 hours post-surgery												
Screening & Baseline Measures	screening seline ures	Presurgical Intake T-1 hour If not completed at baseline	Cesarean Surgery	Ketamine Infusion 15-45 minutes Post	12-hour Ketamine Infusion 12-hour post-infusion								fusion		
			Cesarear		15 Minutes	30 Minutes	Hour 1	Hour 4	Hour 6	Hour 8	10Hour	Hour 12	Hour 16	Hour 20	Hour 24
Informed consent	Х														
Demographics and Medical History (inc. Opioid use in hospital)	Х	Х													
Concomitant medication review	Х	X													
Administer study intervention				X											
Maternal Plasma Samples a							Χ		Χ		Χ	X			
Adverse event review b				X											X
Surgical operative survey				Х											
Pain Intensity	Х	X													
Pain Unpleasantness	X	X													
PROMIS-PI	X	X													
EPDS	Х	X													
PSS	X	X													
SF-MPQ	Х	X													
RASS b					Х	Χ	Χ	Х		X	X	Х	Х	Χ	X
Patient Vitals b		X		Х	X	Х	Χ	Х	Х	Χ	Χ	Х	Χ	Χ	X
LSD Short b					Х	Х	Х	Х		Х	Х	Х	Х	Х	Х
Side Effect Diary and Patient Acceptability b					Х	Х	Х	Х		Х	Х	Х	Х	Х	Х

<sup>a Maternal Plasma Sampling includes analysis of Ketamine, ketamine metabolites (Nor-Ketamine & DKNK), Ketamine R- & S-isomers, cortisol, prolactin, and CYP3A and CYP2B6 enzymes

b Adverse Events will result in collection of RASS, LSD short form, Patient vitals, Patient Acceptability ratings, and Maternal plasma sampling at any point between infusion start (t = 0) to 24-hours post-infusion start. LSD score of >8 will trigger a notification to staff and investigator to prompt bedside evaluation.

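### An early stop for unresolved sedation or low respiratory rate need not be scored as a DLT, because neither the early cells of Table 1 nor section 3.4.1 requires it

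*Combined protocol and SAP*

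**What the plan says.** Table 1 in section 6.3 has a row triggered by "If RASS -2 or below, OR Respiratory Rate is < 8". The infusion is first held and the patient rechecked every 10 minutes. If there is no resolution within 1 hour, the 2nd-action cell reads "D/C infusion based on investigator discretion and monitor subject for safety as described in Section 7.4 and 7.5", and the 3rd-action cell gives the same instruction. The last column of the row reads "D/C infusion and monitor subject for safety as described in Section 7.4 and 7.5 Event qualifies as DLT". It is the only cell in the row that mentions DLT.

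Section 3.4.1 gives the DLT definition that the design uses. One condition is systolic pressure or heart rate persistently outside limits. The other is "complete infusion cessation due to intolerable side effect acceptability ratings by patient". The intolerable event to which the definition also refers is described in hemodynamic terms only. RASS, sedation and respiratory rate are not listed.

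The escalation rule in the same section is "Escalations occur until 2 in a cohort of 3 to 6 experiences DLT". Section 5.1 states that four dosing schematics will be tested.

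**The concern.** A stop at the 2nd action means the patient stayed deeply sedated, or breathed fewer than 8 times a minute, for an hour with the drug already held. That is at least as serious as the course leading to the last column, where, reading left to right, the event resolved on hold and the infusion continued at a reduced dose. Yet only the later stop is expressly scored.

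The gap is narrower than the whole row, because some early stops already count. Section 5.5 describes a "side effect diary including questions of sedation, LSD short form", the Side Effects text in section 7 places RASS in the digital diary, and Appendix 2 footnote b says "Adverse Events will result in collection of RASS, LSD short form, Patient vitals, Patient Acceptability ratings, and Maternal plasma sampling". A stop that follows the patient's own unacceptable rating meets 3.4.1. What remains is the patient stopped on a clinician's judgement who rates the event acceptable or gives no rating. A missing rating is plausible in someone sedated to RASS -2.

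If that patient is not scored, the dose level can be passed. Below the top level, the next cohort then receives a higher load after an infusion was stopped for unresolved sedation or respiratory depression.

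**Working it through.** **Text, side by side**

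| Situation in the RASS / respiratory rate row | Table 1 | Section 3.4.1 |
|---|---|---|
| Stop at 2nd or 3rd action, patient rates the event unacceptable and is stopped for it | No DLT label | DLT (patient-rated cessation) |
| Stop at 2nd or 3rd action, rated acceptable or not rated | No DLT label | Not listed |
| Stop in last column | DLT | Not listed unless patient-rated |

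The second line is the gap. Clinician-judged unacceptability appears in 6.3 and 9.1, but only as a trigger for dose adjustment or supportive care.

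**The plan's own threshold.** 2/6 = 33.3% and 2/3 = 66.7%, so two events in three to six patients do meet the stated limit of at least 33%. One event in six is 16.7% and does not.

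**Effect of one uncounted stop.** Figure 2 is not available, so the usual 3+3 reading of 3.4.1 and section 4 is assumed: 0/3 escalates, 1/3 adds three patients, at most 1/6 escalates. Let p be the true DLT rate and q = 1 - p.

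- The stop is the only event in the first three. Counted, the level passes only if the next three have none: q³ = 0.67³ = 0.301 at p = 33%, and 0.50³ = 0.125 at p = 50%. Not counted, the result is 0/3 and the level passes with probability 1.
- The stop is the second event in six. Counted, 2/6, probability of passing 0. Not counted, 1/6, probability 1.

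These results need no assumption about how often such stops occur.

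**Illustration 1: a share of DLTs goes uncounted.** P(pass level) = q³ + 3pq²·q³, where the counted rate is p = true rate × (1 - s·u). Here s is the share of DLTs that are early RASS or respiratory stops (assumed 5% to 20%), and u is the fraction of these without an unacceptable patient rating (assumed 50% to 100%). So s·u runs from 0.05 × 0.5 = 0.025 to 0.20 × 1 = 0.20.

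| True DLT rate | All counted | s·u = 0.025 | s·u = 0.20 |
|---|---|---|---|
| 33% | p = 0.330: 0.434 | p = 0.3218: 0.451 | p = 0.264: 0.570 |
| 50% | p = 0.500: 0.172 | p = 0.4875: 0.186 | p = 0.400: 0.309 |
| 12.5% | p = 0.125: 0.862 | p = 0.1219: 0.868 | p = 0.100: 0.906 |

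The 12.5% row borrows the 1/8 in section 6.3 who received a lower rate because of side effects. The protocol does not present it as a DLT rate.

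**Illustration 2: uncounted stops occur on top of the listed DLTs.** Let a be the listed DLT rate and r the per-patient rate of early stops without an unacceptable rating, assumed independent. If counted, p = 1 - (1 - a)(1 - r); if not, p = a. With a = 12.5% the chance of passing is 86.2% if the stops are not counted. If they are counted it is 77.5%, 68.1%, 49.4% or 33.0% for r = 5%, 10%, 20% or 30%. Over a from 0 to 20% and r from 5% to 30%, not counting raises the chance of passing by about 3 to 55 percentage points.

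**The case against.** The strongest reply is that the last column classifies the event, not the action step. Its heading refers simply to non-resolution, and an event unresolved after an hour's hold has not resolved. On this view the early cells say when the investigator may stop, and the end column says how the event is scored. The reading is possible. But the early cells have their own non-resolution condition and their own instruction, without the label. Even on the generous reading, Table 1 would then conflict with the closed list in 3.4.1.

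The opening of section 12 describes DLT more loosely, as unacceptable side effects or adverse events. Section 3.4.1 narrows the relevant adverse event to hemodynamics, so this does not settle the matter. The DSMB and the investigator would see such a stop, but no written rule tells them to score it.

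Three points stand. The remaining case is narrow: a trigger lasting an hour off drug at sub-anesthetic doses, then a stop, and no unacceptable rating. Its frequency is unknown, and at a low true DLT rate or a small share the average effect is slight (86.2% to 86.8% at the low end of Illustration 1). Some of these events could come from intrathecal opioid, rescue hydromorphone or midazolam rather than ketamine.

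The separate nausea or vomiting row also has unlabelled early cells. It is less exposed, because those symptoms are diary items that prompt an acceptability rating and section 6.3 makes no adjustment when they are rated acceptable.

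**Conclusion.** The concern holds and should be fixed. Followed literally, the plan need not score an early clinician-judged stop for RASS -2 or below or respiratory rate under 8 when the patient has not rated the event unacceptable. The plan does not forbid scoring it; it leaves the primary endpoint undetermined in this case.

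One such event can reverse a dose decision. As the sole event in three, the chance of passing goes from 30% (true rate 33%) or 12.5% (true rate 50%) to 100%; as the second event in six, from 0 to 100%. Averaged over trials under the assumed shares of Illustration 1, the chance of passing a level rises from 43% to 45%–57% at a true rate of 33%, and from 17% to 19%–31% at 50%. Those averages rest on assumed frequencies; the per-event results do not. Confidence is medium, because the table can be read another way and the figures are not available.

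**What to change.** Put the last column's DLT label in the 2nd- and 3rd-action discontinuation cells of the RASS / respiratory rate row. Add one condition to the list in 3.4.1: *complete infusion cessation, at any action step, for RASS -2 or below or respiratory rate under 8 not resolved within 1 hour of holding the infusion*. Do not make an unresolved event a DLT when the infusion is not stopped, and leave the timing of the stop to the investigator.

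The cost is wording in two cells and one line. RASS and vital signs are already scheduled in Appendix 2. A few more DLTs may be counted, including some due to opioids or midazolam, so the MTD may come out lower. That is consistent with the last column, which already counts the event without an attribution test.

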#### 6.6 Rescue Medications

Rescue antiemetics will be provided for patients reporting nausea or vomiting. The following medications will be used to treat nausea or vomiting at the time of patient reporting these symptoms:

- Ondansetron 4mg IVP p.r.n. nausea or vomiting or
- Dexamethasone 4-6mg IVP p.r.n. nausea or vomiting
- After a total of two doses of ondansetron or dexamethasone, additional rescue antiemetics will be given at the full discretion of anesthesiologist

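### Two Table 1 rows (nausea or vomiting; low RASS or respiratory rate) count events as DLTs that the definition in 3.4.1 does not recognise

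*Combined protocol and SAP*

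**What the plan says.** Section 3.4.1 defines a DLT by two limbs. One is a hemodynamic event (systolic pressure or heart rate outside stated limits) that persists over three consecutive measurements within 15 minutes. The other is "complete infusion cessation due to intolerable side effect acceptability ratings by patient". Section 4 (MTD dosing protocol) sends the reader to 3.4.1 for the definition. The escalation rule is "Escalations occur until 2 in a cohort of 3 to 6 experiences DLT", and the MTD is the level below.

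The text of 6.3 just above Table 1 names nausea and vomiting among the patient-reported effects. It sends effects rated unacceptable to the table and adds: "If side effects are rated 'acceptable' then no dose delays or adjustments will occur".

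Table 1 then lists nausea and vomiting twice. The general patient-rated row covers dizziness and similar symptoms through "hallucinations, nausea, vomiting, or other side effects rated by patient as Not Acceptable", and its first action is an immediate 10-minute hold. A further row is headed only with nausea or vomiting. Its first action is a rescue antiemetic under 6.6, then "Re-evaluate for symptom resolution 10 min after rescue medication", then the 10-minute hold. From the second action on, the two rows match, and both end in discontinuation counted as a DLT.

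A third row, for RASS -2 or below or respiratory rate below 8, follows the same hold-and-halve path and also ends in a DLT. It contains no patient rating.

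**The concern.** The DLT count decides the primary endpoint, and the plan gives two rules for it that do not agree. Staff at the bedside will work from Table 1, while whoever scores the cohort will work from 3.4.1. A patient taken off the infusion for persistent nausea that she still calls acceptable is a DLT under the table row as written, but not under 3.4.1. A patient taken off for persistent deep sedation or slow breathing is a DLT under the table and falls in neither limb of 3.4.1. With at most 12 patients planned, a single disputed event can decide whether a dose level passes.

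The double listing of nausea and vomiting adds a smaller problem. Even if a rating is always required, unacceptable nausea fits two rows, and the table text does not say whether the antiemetic and 10-minute recheck come before the hold.

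**Working it through.** The plan states no figure on this point and made no power calculation, so the check compares the rules and then shows how much one event can matter.

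**Step 1: Table 1 against 3.4.1.**

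| Table 1 event | Patient rating required in the row? | Row ends in a DLT? | Recognised by 3.4.1? |
|---|---|---|---|
| Persisting hemodynamic event | Not applicable | Yes | Yes, first limb |
| RASS -2 or below, or respiratory rate < 8 | No | Yes | No |
| Patient-rated side effects, including nausea and vomiting | Yes | Yes | Yes, second limb |
| Nausea or vomiting (separate row) | No | Yes | Only if the infusion stopped because of an intolerable rating |

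Applying the 6.3 acceptability rule to the whole table would cure the last row. It would not cure the RASS/respiratory row, because RASS and respiratory rate are not among the patient-reported effects that 6.3 lists and that row asks for no rating.

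**Step 2: effect of one event.** The rule in 3.4.1 stops escalation at 2 DLTs in 3 to 6 patients. A cohort with one undisputed DLT has 1/6 = 16.7% and passes. If one disputed event is also counted, it has 2/6 = 33.3% and stops, and the MTD becomes the level below.

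**Step 3: sensitivity to an added DLT rate.** Assume the standard 3+3 rule (Figure 2 was not available to me) and a true DLT probability p at a level:

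P(stop) = [3p²(1−p) + p³] + 3p(1−p)² × [1 − (1−p)³]

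For p = 0.10: 0.028 + 0.243 × 0.271 = 0.0939. For p = 0.12: 0.0397 + 0.2788 × 0.3185 = 0.1285.

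The table shows P(stop) when the wider labels add 0, 1, 2 or 5 percentage points to p. Every p and every addition is an assumption.

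| True rate under 3.4.1 | +0 | +1 | +2 | +5 |
|---|---|---|---|---|
| 5% | 2.7% | 3.7% | 5.0% | 9.4% |
| 10% | 9.4% | 11.1% | 12.9% | 18.6% |
| 20% | 29.1% | 31.3% | 33.5% | 40.0% |

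**Step 4: size of the first-action difference.** Suppose unacceptable nausea is reported during the one-hour load and is unresolved at the 10-minute recheck. Under either row there is then one 10-minute hold and a 50% cut to the end of the hour. The fraction of the load delivered is (full-rate minutes + 0.5 × half-rate minutes)/60.

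- Report at 15 minutes: immediate hold (15 + 0.5 × 35)/60 = 54.2%; recheck first (25 + 0.5 × 25)/60 = 62.5%.
- Report at 30 minutes: immediate hold (30 + 0.5 × 20)/60 = 66.7%; recheck first (40 + 0.5 × 10)/60 = 75.0%.

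The gap is 10 × 0.5/60 = 8.3 points of the load. That is 0.083 × 0.05 = about 0.004 mg/kg at the first level, and 0.083 × 0.2 = about 0.017 mg/kg at the protocol's ceiling of 0.2 mg/kg/hr.

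**The case against.** The best defence is that the plan already settles the nausea question. Section 4 names 3.4.1 as the definition, the acceptability rule stands directly above the table, and every positive diary item triggers a rating, so the rule can always be applied. The version 7.0 log says the table's DLT entries were meant to follow the revised definition; I cite it for intent only. Figure 3, described as the decision chart for acceptability-based dosing, may also set the order of steps. On that reading, counting accepted nausea as a DLT would misapply the plan, and the separate row exists only to add the antiemetic step. Most of this stands, and the gated reading is probably intended. But the row as written carries no condition, while its neighbour does, and that invites the reader to take the difference as deliberate.

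The defence does not reach the RASS/respiratory row. Section 12 does describe dose-limiting toxicity loosely as unacceptable side effects or adverse events, but 3.4.1 limits the adverse events in its tolerability definition to hemodynamic ones.

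A reader might infer three stronger points, and the documents do not support them.

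- That unacceptable nausea could be left to the drug for these symptoms in 9.1 ("Midazolam 1-4mg IVP p.r.n. dysphoria, at discretion of managing anesthesiologist"), because the patient-rated row says "Supportive care medications in 9.1". Section 6.6 removes this: "Rescue antiemetics will be provided for patients reporting nausea or vomiting", whichever row is used.
- That the one-hour persistence condition in the 6.3 trigger list postpones every adjustment until after the loading hour. That item also says the effect persists despite a minimised infusion rate, so it presupposes an earlier reduction.
- That the antiemetic row spares the whole load when rescue works. The cell does not say that the hold depends on rescue failing.

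**Conclusion.** The point holds as an inconsistency between stated rules for classifying the primary endpoint. It is firm for the RASS/respiratory row. For the nausea or vomiting row it is an unconditional wording that probably does not reflect the intent.

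At the level of a single cohort the consequence is one dose level: 1/6 becomes 2/6. On average it is likely to be small. The nausea route needs symptoms that outlast antiemetics, holds and cuts in a patient who still rates them acceptable, after routine antiemetic prophylaxis. The documents give no rate for this or for persistent low RASS or respiratory rate. The stopping probabilities above rest on assumed rates and a standard 3+3 rule.

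The double listing of nausea matters less: at most a 10-minute difference in when the hold starts, or 8.3 points of the load in the illustration. It would go too far to conclude that the MTD is biased downward, since no rate supports that and holds and cuts occur in every row of the table.

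**What to change.** Three wording changes, with a check that Figure 3 agrees:

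1. Keep one nausea/vomiting row. Any report receives a 6.6 antiemetic and a 10-minute recheck. The hold, the 50% cuts, discontinuation and the DLT label apply only if the patient rates the effect Not Acceptable.
2. Delete nausea and vomiting from the general patient-rated row, so that each report falls under one row.
3. Add to the DLT list in 3.4.1 discontinuation for persistent RASS -2 or below or respiratory rate below 8, so that the definition matches Table 1.

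The cost is an amendment of wording. No new data are needed for the acceptability condition, because any positive diary item already prompts the rating, and RASS and vital signs are already scheduled in Appendix 2. The one downside is a slightly broader DLT definition in 3.4.1.
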